The PRECISe trial is a bi-national, quadruple-blinded, multicenter randomized controlled trial (RCT) assessing the superiority of high versus standard enteral protein provision in mechanically ventilated ICU patients. (2)

Randomization

A computer algorithm was used to generate the concealed, random allocation sequence. Patients were randomized in a 1:1 ratio, stratified per center, using block randomization with random permuted block sizes varying between 4 and 6.

Sample size

The sample size calculation was based on a published cross-sectional measurement of the EQ-5D-5L health utility score at 180 days following ICU admission, as longitudinal data were unavailable (3). A minimum difference of 0.06 points on the EQ-5D-5L health utility score was selected to represent the minimum clinically important between-group difference to be detected. (4)

Based on these data, the sample size for the PRECISe trial was calculated as follows: assuming a standard deviation (SD) of 0.3 at 180 days (3), considering a two-sided type I error rate α of 5% and a type II error rate β of 20% (yielding a statistical power of 80%), 392 participants per intervention group will be required to detect the minimum clinically important difference of 0.06 in the EQ-5D-5L health utility score. In line with other critical care trials, the sample size has been adjusted upwards for an estimated 5% loss to follow-up for the primary endpoint. (5) After this adjustment, the final sample size for the PRECISe trial was set at 824 participants.

During the preplanned interim safety analysis after inclusion of 50% of patients, it became apparent that mortality was higher than anticipated, resulting in a standard deviation of the EQ-5D-5L HUS that was larger than expected (0.38 vs 0.30). Since this potentially could reduce the power of the study, the DSMB advised to increase the sample size. By running a Monte Carlo simulation of the primary outcome analysis using raw longitudinal data of the actual study population at that time (n = 709), without unblinding, it was calculated that with the observed standard deviation, a sample size of 935 patients would be required to retain 80% power to detect the minimally important difference of 0.06, while correcting for the actual loss-to-follow-up rate of 9.4%.

Framework

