Following enrolment of 50% of the targeted sample size, a preplanned interim safety analysis was performed by the Data Safety Monitoring Board (DSMB). All analyzed data were blinded to treatment allocation. The safety data analyzed were ICU mortality and in-hospital mortality. No other differences in outcome measures of effectiveness were assessed. In addition, the DSMB received accumulating information relating to recruitment, data quality, missing data, and protocol compliance. The independent blinded DSMB statistician performed all analyses. The study would have been terminated if the rate of safety endpoints in any of the feeding labels was more than twofold the rate in the other feeding labels. The DSMB reserved the right to make additional recommendations regarding the execution of the trial, as per DSMB charter. No other interim analyses were planned. The preplanned interim safety analysis revealed no safety issues.

Section 4. Statistical Principles

General rules of statistical reporting

Categorical data will be presented as counts and percentages. Continuous variables will be described as mean and standard deviation if data are approximately normally distributed, and median and interquartile range (first and third quartile) otherwise. Normality will be assessed visually using histograms and pp- or qq-plots.

Confidence intervals and *P* values

Effect sizes with 95% confidence intervals will be reported, together with a 2-sided P-value. The alpha used for testing will be set at 0.05 in all cases except for testing for interactions. In that case, an alpha of 0.10 will be used. No adjustments for multiplicity will be carried out.

Adherence and protocol deviations

Adherence to the intervention

Per protocol, the intervention should have been initiated within 48 hours of ICU admission at 25% of the calculated target and increased by 25% per day until 100% of energy and protein targets were reached on day 4. Targets were set at 25 kcal/kg/day, using the patient's weight at admission. For those with a BMI >27 kg/m², the ideal body weight (defined as 27 x height²) was used. The study nutrition was continued for the duration of ICU stay if enteral nutrition was required or until a maximum of 90 days.

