As sensitivity analysis, the model will be further adjusted for sex, APACHE II score, APACHE IV admission diagnosis, and NRS-2002.

Secondary and tertiary outcomes

Survival outcome

For the secondary endpoint overall survival, survival curves for both treatment arms will be constructed using the Kaplan-Meier method. Then, a Cox proportional hazards frailty model, with a 2-level structure, i.e., participants clustered within centers, will be used to investigate a treatment effect. The crude, unadjusted Hazard ratios will be reported with a 95% confidence interval. The proportional hazard assumption will be assessed as the association between the scaled Schoenfeld residuals and follow-up time. Additionally, sensitivity analyses will be performed by adjusting for potential confounders (sex, APACHE II score, APACHE IV admission diagnosis, and NRS-2002) is similar as described for the primary endpoint analysis.

Longitudinally assessed outcomes

The treatment effects for longitudinally assessed secondary and tertiary endpoints (SF-36, HADS, IES-R, EQ-5D-5L (EQ-VAS and pain question), 6-minute walking distance, MRC-SUM, and handgrip strength, frailty assessed by Rockwood Clinical Frailty Scale and mean and maximum SOFA scores) are assessed using linear mixed-effects models. The statistical approach will be similar as described for the analysis of the primary endpoint, particularly concerning the calculation of between-group differences, the 3-level model structure (with fixed treatment effect and random effects for center and participants), reporting of effect size, adjustment for potential confounders, and model selection strategy.

Time-to-event outcome

For time-to-discharge-alive from hospital, data of non-survivors will be censored at a time point beyond that of the last surviving patient to account for death as a competing risk. Between-group differences will then be estimated similar to overall survival.

Categorical outcomes

The differences in all categorical tertiary outcomes (see **Appendices 3-5**) will be analyzed using Pearson's chi-square test or Fisher's exact test, as appropriate. The treatment effects on all other tertiary outcomes will be analyzed using the Student's t-test or Mann-Whitney U test, depending on the distribution of data.

Subgroup analyses

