Given the mixture distribution of the EQ-5D-5L (the component of zero and the component other than 0), we will specify separate priors per longitudinally assessed outcome. Consequently, we will specify a prior for the mean difference with an EQ-5D-5L other than 0 and a prior for the proportion of patients who have an EQ-5D-5L score of 0 (i.e., deceased patients). This longitudinal analysis will be performed with adjustment for center as a random effect. The results of the analyses for the components will be presented separately and as weighted averages.

Analysis of longitudinally assessed secondary outcomes

Secondary outcomes for which no prior evidence was available will be estimated under a weakly informative prior, in a model similar to the longitudinally assessed primary outcome, with adjustment for the random effect of center.

Analysis of outcomes at one given time point

Secondary binary outcomes, such as 60-day mortality, will be expressed in ORs and absolute risk differences (ARD). These binary outcomes will be analyzed in a binary mixed regression model (Bernoulli distribution) with an adjustment for the random center effect. Priors for these binary outcomes are presented on the log OR scale in Table 1. Other secondary continuous outcomes, such as the duration of mechanical ventilation, will be reported in mean differences (MD) for the specific units of that endpoint. Finally, the abovementioned mixture distribution (the component of zero, and the component other than 0) will be used for the EQ-5D-5L assessment at the cross-sectional time points, and separate priors will be formulated, similar to the primary outcome assessment.

Handling of missing data

As the missingness of data is assumed to be missing at random (MAR), the linear mixed effects model will be appropriate to handle missing data.

Model settings and diagnostics

The models for our analysis will be implemented in *JAGS* using Markov Chain Monte Carlo (MCMC) algorithms, through the *R2jags* package (20, 21). Assessment of model convergence will be performed for key model parameters via potential scale reduction factors (Rhat) effective sample size (ESS), and other diagnostics such as density and trace plots. Model fit will be assessed in relative terms through the deviance information criterion (DIC and other criteria alike), and in absolute terms using posterior prediction checks (PPCs).

(Serious) Adverse events

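### Binary and most non-longitudinal tertiary outcomes, fixed-day mortality among them, are tested without centre, the randomisation stratum, so the tests are mildly conservative if centres differ

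*SAP*

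**What the plan says.** **Randomisation** (SAP Section 2, Randomization): "Patients were randomized in a 1:1 ratio, stratified per center, using block randomization with random permuted block sizes varying between 4 and 6".

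**Tertiary tests** (SAP Section 5, Analysis methods, Categorical outcomes): differences in the categorical tertiary outcomes "will be analyzed using Pearson's chi-square test or Fisher's exact test, as appropriate". The same paragraph adds: "The treatment effects on all other tertiary outcomes will be analyzed using" a t-test or a Mann-Whitney test, chosen by how the data are distributed. It names no centre term and no effect measure. The tertiary list includes hospital mortality and mortality at 30, 60 and 90 days.

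**Where centre is modelled.** The primary model nests participants in centres. Overall survival uses a Cox frailty model with centre as the upper level. The longitudinal outcomes, including the tertiary Rockwood scale and SOFA scores, have a random centre effect. Time to discharge alive follows the overall survival method. In the Bayesian section, binary outcomes such as 60-day mortality "will be analyzed in a binary mixed regression model (Bernoulli distribution) with an adjustment for the random center effect". The Priors subsection extends the centre adjustment to every Bayesian analysis, which includes duration of ventilation.

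**General reporting rule** (SAP Section 4, Confidence intervals and P values): "Effect sizes with 95% confidence intervals will be reported, together with a 2-sided P-value".

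**The concern.** Stratified blocks balance the arms within each centre, so differences between centres contribute almost nothing to the treatment comparison. An unadjusted test still counts those differences as noise. Its standard error is then too large, its true size falls below 5%, and it loses some power. For an efficacy claim this error is on the safe side. For mortality and the harm outcomes it is not, because a real difference becomes slightly easier to miss.

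The plan is also inconsistent with itself. It analyses 60-day mortality and ventilation duration twice, with centre in the Bayesian model and without it in the frequentist test. If the two results differ, the reader cannot tell whether the prior or the centre term is responsible.

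**Working it through.** The SAP gives no operating figure for the tertiary tests, so there is none to reproduce.

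**Inputs from the SAP:** 1:1 allocation in blocks of 4 to 6 within centre; two-sided alpha 0.05; 935 patients after the sample-size increase.

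**Assumptions, not in the SAP:** event rate in an average centre of 10% to 30%; between-centre SD on the log-odds scale of 0.3 to 0.8; for the simulation, 5, 10 or 20 centres of equal size.

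**Step 1, size.** Let r be the mean within-centre p(1-p) divided by the total p(1-p), with normally distributed centre effects on the logit scale. The unadjusted test rejects when the correctly scaled statistic exceeds 1.96/√r, so

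size = 2 × [1 − Φ(1.96/√r)].

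**Step 2, power.** A centre-adjusted test with 80% power has expected statistic 1.960 + 0.842 = 2.802. For the unadjusted test,

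power = Φ(2.802 − 1.96/√r).

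| Event rate | Centre SD | r | 1.96/√r | True size | Power |
|---|---|---|---|---|---|
| 10% | 0.3 | 0.992 | 1.968 | 4.9% | 79.8% |
| 30% | 0.3 | 0.981 | 1.978 | 4.8% | 79.5% |
| 10% | 0.8 | 0.932 | 2.031 | 4.2% | 78.0% |
| 30% | 0.8 | 0.887 | 2.081 | 3.7% | 76.4% |

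In the worst row the standard error is too large by 1/√0.887 = 1.062, about 6%. In the mildest it is about 0.4%.

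**Step 3, continuous outcomes.** Here r = 1 − ICC. The same formula gives a size of 4.9% at ICC 0.01, 4.4% at 0.05 and 3.9% at 0.10.

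**Step 4, simulation check.** Trials of 935 patients were generated with centre-stratified blocks of 4 or 6 and a 30% event rate. Each scenario had 20,000 trials under the null and 8,000 under an assumed odds ratio of 0.68. Ranges run over the three numbers of centres.

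| Centre SD | Size, chi-square | Power, chi-square | Power, CMH by centre |
|---|---|---|---|
| 0 | 4.9-5.1% | 74-75% | 74% |
| 0.42 | 4.6% | 72% | 73% |
| 0.6 | 4.3-4.5% | 69-70% | 71-72% |
| 0.9 | 3.5-3.7% | 65-66% | 69-70% |

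The Cochran-Mantel-Haenszel (CMH) test held a size of 4.8-5.1% throughout. The power difference was about 1 point at SD 0.42, 2 points at 0.6 and 4 points at 0.9, the last lying outside the assumed range above. At SD 0 the two tests agreed, so in these scenarios stratifying carried no visible power penalty.

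**The case against.** Several parts of the opposing case stand.

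- **Scope.** A reader might infer that every tertiary outcome ignores centre. The SAP does not support that: the Rockwood scale, SOFA and time to discharge alive have centre in their models. Overall survival to 180 days, a secondary outcome ranked above the fixed-day counts, also includes centre and yields a hazard ratio with a 95% CI. The main mortality comparison is therefore unaffected.
- **Effect sizes.** A reader might infer that the tertiary outcomes will be reported without effect sizes, against the general rule in Section 4. Naming a test does not cancel that rule, and a t-test yields a mean difference with an interval. What is missing is only the choice of measure (risk difference, risk ratio or odds ratio) for binary outcomes, and an estimate to go with the Mann-Whitney test.
- **Size.** A reader might take the conservatism as established. It depends wholly on between-centre variation, on which the SAP is silent, and it vanishes if centres are alike. Even the worst assumed case costs about 4 points of power, and type I error is never inflated.
- **Cost of adjusting.** Some listed events, such as ischaemia or bleeding, may be rare. Centres without events drop out of a CMH test, and mixed logistic models may fail to converge. Adjustment is not free and needs a fallback rule.

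The argument that a simple test is acceptable for supplementary outcomes has some force. It does not explain why two of these outcomes are centre-adjusted in one part of the plan and not in another.

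**Conclusion.** The point holds for the binary tertiary outcomes and for the continuous ones that are neither longitudinal nor time-to-event. Their frequentist tests leave out the factor by which patients were randomised, unlike the other models in the same plan. If centres differ, the tests are mildly conservative: a true size of about 3.7-4.9% and about 76-80% power where an adjusted test would have 80%. Those ranges rest on assumed event rates of 10-30% and a centre log-odds SD of 0.3-0.8. The mismatch with the Bayesian handling of 60-day mortality and ventilation duration rests on no assumption. Priority is low: the outcomes are tertiary, and no primary or secondary conclusion changes.

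**What to change.** Amend the Categorical outcomes paragraph in SAP Section 5:

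- **Binary tertiary outcomes:** report a Mantel-Haenszel risk difference or odds ratio stratified by centre, with its 95% CI and the CMH test. Name one measure in advance; this also settles the open choice under the general reporting rule.
- **Non-longitudinal continuous outcomes:** use a linear mixed model with a random centre effect, or the van Elteren test where the distribution calls for ranks. For ventilation duration, the mixed model's mean difference is the one that lines up with the Bayesian analysis.
- **Sparse events:** keep Fisher's exact test as the fallback, with the event count that triggers it stated beforehand.
- **No change** for the Rockwood scale, SOFA and time to discharge alive.

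Fix the wording before the randomisation labels are paired after database lock. The cost is the fallback rule and slightly more analysis work. No new data and no change in sample size are needed.

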Adherence to the intervention will be presented for the intervention and control group as daily mean (± SD) and median (interquartile range, IQR) protein and calorie delivery over the first 10 days after randomization. In addition, the daily percentage of target (i.e., nutritional adequacy) per treatment arm and a summary value for the entire study period (number of feeding days and percentage of total study target provided) will be reported. Total intake will be calculated as the sum of all calories and protein from enteral and parenteral nutrition, supplemental protein, and amino acids for all days where intake could completely be quantified, i.e. excluding days with oral intake.

The following parameters relating to protocol adherence, will be reported:

- Time from ICU admission to randomization
- Time from ICU admission to start of intervention

- Number of days receiving study nutrition
- Total protein adequacy (g of protein received versus prescribed), reported separately for day
 1, day 2, day 3, and day 4 and onwards from randomization (up to ten days)
- Total energy adequacy (kcal received versus prescribed), reported separately for day 1, day 2, day 3, and day 4 and onwards from randomization (up to ten days)
- Number of patients receiving on average <80% of prescribed protein over the entire ICU stay
- Number of patients receiving on average 80-110% of prescribed protein over the entire ICU stay
- Number of patients receiving on average >110% of prescribed energy over the entire ICU stay

Protocol deviations

The following protocol deviations will be reported:

- Number of patients who did not fulfil all inclusion criteria or fulfilled one or more of the exclusion criteria
- Number of patients in whom invasive mechanical ventilation was initiated more than 48 hours after ICU admission
- Number of patients who were not randomized within 72 hours of ICU admission
- Number of patients of Belgian sites for whom no written informed consent was obtained
- Number of patients who received the incorrect intervention at any time during the treatment phase
- Number of patients who received parenteral nutrition in the first 7 days of ICU admission

Analysis populations

Intention-to-treat

Since it is a superiority trial, all analyses will be performed on an intention-to-treat (ITT) basis. The ITT population will include all randomized patients as per allocated treatment arm.

Per-protocol

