- 30-, 60-, and 90-day mortality: number of patients who died within 30, 60, and 90 days after ICU admission.
- Time-to-discharge-alive from hospital: number of days until live hospital discharge.
- Days alive and at home at day 90 (DAAH₉₀) after index ICU admission.
- Nutritional adequacy: the ratio between the total amount of calories and grams of protein actually received by patients and prescribed during the treatment period.
- Duration of mechanical ventilation: number of days on invasive mechanical ventilation.
- Duration of index ICU stay: number of days of index ICU admission.

- Incidence of ICU readmissions: number of patients readmitted to the ICU during index hospital stay and number of readmissions per patient.
- Administration of prokinetics: number of patients who received a prokinetic and number of days receiving a prokinetic drug.
- Incidence of gastrointestinal intolerance/symptoms: number of patients who experienced, at any time during index ICU stay, vomiting, ischemia, diarrhoea, abdominal distention, gastric paresis, or bleeding/ ulcer.
- Incidence of ICU-acquired infections: number of patients who contracted an ICU-acquired infection.
- Incidence of acute kidney injury: number of patients with Acute Kidney Injury (AKI), defined as a serum creatinine level higher than 2 times baseline level.
- Incidence and duration of renal replacement therapy: number of patients who received renal replacement therapy and number of days on renal replacement therapy.
- Incidence of hepatic dysfunction: number of patients with hepatic dysfunction, defined as a total bilirubin level > 3 mg/dL.
- Sequential Organ Failure Assessment (SOFA) score: mean and maximum SOFA score during first two weeks of index ICU admission.
- The difference in mobilization treatment: number of days and degree of daily mobilization (e.g., passive, active, in-bed cycling, out-of-bed, etc.).
- Duration of index hospital stay: number of days of index hospital admission.
- Destination of hospital discharge: i.e., home, rehabilitation center, care facility, etc.
- Length of stay at rehabilitation facility: number of days at a rehabilitation center.

Functional outcomes

- Frailty assessed by Rockwood Clinical Frailty Scale: ranges from 1 to 9, with higher scores indicating increasing frailty, collected at 30, 90, and 180 days after ICU admission.

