Mechanical ventilation	Total duration of invasive mechanical ventilation during index ICU	Continuous
duration	admission in days	
Reintubation	Reintubation during index ICU admission & duration of subsequent	Binary,
	ventilation episode(s)	continuous
ICU acquired infection	ICU-acquired infection during index ICU admission	Binary
Ventilator acquired pneumonia	Ventilator-acquired pneumonia during index ICU admission	Binary
Acute Kidney Injury	Defined as creatinine level higher than 2 times baseline level	Binary
Acute Runey injury	(including start of Renal Replacement Therapy) during index ICU	Dinary
	admission	
Refeeding	Defined as phosphate levels below <0.65 mmol/l, a drop >0.16	Binary
hypophosphatemia	mmol/l from the previous level in ICU and no other explanation for	
	hypophosphatemia during index ICU admission	
Hepatic dysfunction	Defined as cholestasis and liver dysfunction, i.e., bilirubin level	Binary
	higher than 3 mg/dl or 51,3 $\mu mol/l$ during index ICU admission	
Vomiting	Vomiting during index ICU admission	Binary
Ischaemia	Ischaemia during index ICU admission	Binary
Diarrhoea	Diarrhoea during index ICU admission	Binary
Abdominal distension	Abdominal distension during index ICU admission	Binary
Gastric paresis	Gastric paresis during index ICU admission	Binary
Bleeding/ulcer	Bleeding or ulcer during index ICU admission	Binary
Renal replacement	Continuous veno-venous hemofiltration (CVVH) or intermittent	Binary,
therapy	hemodialysis during index ICU admission, including duration in	continuous,
	days and type of anticoagulation	nominal
ECMO	Extracorporeal membrane oxygenation (ECMO) during index ICU	Binary,
	admission, including duration in days and type of cannulation	continuous,
		nominal
SAE	Any Serious Adverse Event (SAE) during index ICU admission	Binary
Concomitant	Type and duration in days of administered IV antibiotics,	Nominal,
medication	prokinetics, glucocorticoids or muscle relaxants during index ICU stay	continuous
ICU admission	Duration of index ICU admission in days	Continuous
duration		
ICU discharge location	Location where the patient is discharged to after index ICU admission	Nominal
	umsion	

ICU readmission	ICU readmission during index hospital admission, including reason	Binary,
	and duration of subsequent ICU admissions in days	nominal,
		continuous
Hospital admission	Duration of index hospital admission in days	Continuous
duration		
Hospital discharge	Location where the patient is discharged to after index hospital	Nominal

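### Ventilation days and ICU days are compared with no rule for death, so any difference in mortality or its timing is mixed into the result (minor)

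*SAP*

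**What the plan says.** Under Tertiary outcomes the SAP lists "Duration of mechanical ventilation: number of days on invasive mechanical ventilation" and "Duration of index ICU stay: number of days of index ICU admission". Appendix 3 repeats both as continuous variables: "Total duration of invasive mechanical ventilation during index ICU" admission, and "Duration of index ICU admission in days". It also records reintubation and the length of later ventilation episodes.

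Neither outcome is categorical, neither is among the longitudinal outcomes, and neither is the named time-to-event outcome. Both therefore fall under the closing sentence of Secondary and tertiary outcomes, which assigns everything left over to "t-test or Mann-Whitney U test, depending on the distribution of data". Under Analysis populations, all analyses are by intention to treat: "The ITT population will include all randomized patients as per allocated treatment arm".

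Death has an explicit rule in two places. Decedents score 0 on the EQ-5D-5L utility (Withdrawal/follow-up). For time to live hospital discharge, "data of non-survivors will be censored at a time point beyond that of the last surviving patient to account for death as a competing risk" (Time-to-event outcome). A further tertiary outcome, "Days alive and at home at day 90", reflects death by its construction. The Missing data section does not fill the gap, because a decedent's day count is observed, not missing.

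**The concern.** Death ends the count of ventilated days and of ICU days. A patient who dies ventilated on day 4 contributes 4 days, the same as one who is weaned on day 4 and recovers. A t-test or a rank test on the raw counts cannot tell them apart. If the arms differ in how many patients die, or in when they die, the difference in days reflects mortality as well as recovery, and a reader cannot separate the two.

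The SAP recognises this for hospital discharge but not for two durations exposed to the same competing event. At stake is the reading of two tertiary comparisons, which will be reported with confidence intervals and P values. The primary outcome is not involved.

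**Working it through.** The SAP gives no figure for these two outcomes, so there is none to reproduce. What can be checked is how large the mixing could be.

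**Inputs from the SAP**
- 935 patients, 1:1 (Sample size, Randomization): about 467 per arm.
- Literature-based prior for 60-day mortality: log odds ratio with mean -0.02 and SD 0.09 (Priors table).
- Minimal important difference for ventilation: 1.0 day (same table).

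**Assumptions, because the SAP gives no values**
- 27% mortality in one arm.
- Two-thirds of deaths occur on ventilation.
- Weaning is identical in both arms.
- Each death on ventilation cuts off about 3 to 17 ventilated days.

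**Step 1: shift in mean ventilation days when death cuts stays short.** Shift = extra share dying on ventilation × days cut off per such death.
- 27% v 30% mortality: 18% v 20% die on ventilation. 0.02 × 3 = 0.06 and 0.02 × 17 = 0.34, so about 0.1 to 0.3 day.
- 27% v 32%: 18% v 21.3%. 0.033 × 3 = 0.10 and 0.033 × 17 = 0.57, so about 0.1 to 0.6 day.
- Equal mortality and timing: 0.

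With constant weaning and death rates the days cut off equal 1/(weaning rate). Rates of 0.06 and 0.12 per day give 16.7 and 8.3 days, so the 5-point gap gives 0.033/0.06 = 0.56 and 0.033/0.12 = 0.28 day, inside the range.

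**Step 2: effect on the test.** Trials were simulated with 467 per arm and no true difference in weaning, under a range of models for liberation and death times. The table gives the share of trials in which the higher-mortality arm is significantly favoured (2.5% expected by chance).

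| Dying on ventilation | Mann-Whitney | t-test |
|---|---|---|
| 18% v 18% | 2.1-2.7% | 2.1-2.8% |
| 18% v 20% | 3.3-7.1% | 3.0-7.3% |
| 18% v 21.3% | 3.6-12.7% | 3.2-14.3% |

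A separate simulation used log-normal liberation (median 10 days, log SD 0.8), 30% v 35% mortality, and median day of death 4, 7, 10 or 20. The shifts were 0.44, 0.36, 0.30 and 0.19 day, and Mann-Whitney favoured the worse arm in 13%, 9%, 7% and 3% of trials.

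**Step 3: how likely are such gaps?** On the logit scale 27% is -0.995, 30% is -0.847 and 32% is -0.754.
- Rise of at least 3 points: z = (0.147 + 0.02)/0.09 = 1.86, probability about 3%.
- Rise of at least 5 points: z = (0.241 + 0.02)/0.09 = 2.90, probability about 0.2%.
- Averaged over the prior (weaning 0.06 to 0.12 per day), the mean absolute shift is 0.08-0.16 day with two-thirds of deaths on ventilation and 0.12-0.24 day with all of them.

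**Step 4: ICU stay.** Assume 80% of deaths occur in the ICU and live discharge at 0.04 to 0.08 per day. A 3-point gap gives 0.024/0.08 = 0.30 to 0.024/0.04 = 0.60 day. A 5-point gap gives 0.04/0.08 = 0.50 to 0.04/0.04 = 1.00 day.

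**Step 5: the reverse case.** Suppose decedents are ventilated longer than survivors: medians 14 v 8 days, log-normal with log SD 0.8. The means are 14 × exp(0.32) = 19.3 and 8 × exp(0.32) = 11.0. At 30% v 40% mortality, 0.10 × 8.3 = 0.83 day. Simulation gave 0.81 day, with the higher-mortality arm looking worse; it had the lower mean in only 20% of trials.

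**The case against.** The strongest reply is that this matters little. The outcomes are tertiary. Overall survival, mortality at several time points, time to live discharge and days alive and at home are all reported beside them. Averaged over the SAP's own prior, the shift is a small fraction of the 1.0-day important difference. The interim safety analysis raised no issue, and nothing in the SAP says that raw days will be read alone as evidence of benefit. All of this stands and sets the grade at minor. It does not supply the missing rule, since none of the other outcomes measures ventilation or ICU stay.

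A second reply is that the remedy also mixes in mortality, and more often. With identical weaning, the late-censored comparison favours the lower-mortality arm in 6-11% of trials at 18% v 20% and 12-22% at 18% v 21.3%. That is correct and must be disclosed. The remedy does stop rewarding death: with unequal mortality, the higher-mortality arm was favoured in at most 1.1% of trials. Raw days remain a legitimate description of resource use, and the costing needs them.

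A third reply is that liberation is undefined when patients are reintubated. This stands, and the fix addresses it.

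Two stronger readings are tempting. A reader might infer that the plan errs in a known direction, always flattering the arm with more deaths. The SAP gives no durations for decedents and survivors, and the reverse case above shows that the sign can change. A reader might also infer that the Bayesian analysis of ventilation days has the same gap. The SAP refers that analysis to a separate published protocol that is not at hand and may state a rule, so no fault can be claimed there.

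**Conclusion.** The concern holds as a minor point. As written, the two comparisons mix mortality with recovery whenever mortality or its timing differs between arms, and the sign depends on whether decedents have shorter or longer stays than survivors. With equal mortality and timing nothing is lost.

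The SAP says that mortality was higher than anticipated but gives no rate, and it reports no difference between arms. The sizes above are therefore illustrations under stated assumptions, not estimates for this trial. A reader should not infer that these comparisons are in fact biased here.

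**What to change.** - Base the between-arm comparison on time to liberation from ventilation alive and time to ICU discharge alive, using the late-censoring method and centre frailty model already planned for hospital discharge.
- Define liberation with regard to the reintubation episodes in Appendix 3, for example as the end of the last ventilation episode of the index ICU stay, and say how a death after that point counts.
- Keep raw days, overall and by survival status, as description and for the health economic evaluation. State that they are not to be read as evidence of benefit.
- State that the new measures are composites that also reflect mortality, do not isolate weaning, and must be read beside the mortality results.

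The cost is a short paragraph of SAP text, a definition of liberation to agree before unblinding, and reuse of the analysis code planned for hospital discharge. The price in interpretation is a hazard ratio, which is less intuitive than a difference in days.
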